5.9.7.2 Genomics Analyses

Genetic variation may contribute to the PK or PD response to a drug. Analyses of buffy coat DNA may include genome-wide studies, including (but not limited to) to the generation of variant data and/or genomic sequencing in hypothesis-generating studies. Additional details regarding the statistical methods for the genomic analyses will be described in a separate protocol.

5.9.7.3 Other Omic Analyses

Epigenetic variation such as DNA methylation has the capacity to contribute to the PD or PK response to a drug. Moreover, profiling metabolites in biofluids may have utility in the identification of circulating PD biomarkers. The generation of additional omics profiles (e.g., metabolomics and methylomics) from an alternative biospecimen such as urine can inform on the utility of these technologies for PD biomarker identification and the analytical framework required for future studies involving this biospecimen. These analyses may also inform on biofluid specificity. These analyses will be considered hypothesis-generating. Additional details regarding the statistical methods for the omics analyses will be described in a separate protocol.

5.9.8 Safety Analyses

5.9.8.1 Adverse Events

All AEs will be coded using the latest version of the Medical Dictionary for Regulatory Activities. The incidence of TEAEs, organized by system organ class and frequency, will be summarized by seriousness, severity, relationship to treatment, and by treatment at onset of the TEAE. A detailed listing of serious AEs and TEAEs leading to withdrawal will also be provided.

5.9.8.2 Clinical Laboratory Tests

Clinical laboratory results (hematology, serum chemistry, and urinalysis) will be summarized using descriptive statistics (number of subjects, mean, SD, minimum, median, and maximum). Clinical laboratory results will be classified as normal or abnormal, according to the reference ranges of the individual parameter. The number and

percentage of subjects with abnormal laboratory results will be provided. No statistical testing will be performed on clinical laboratory data.

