5.2.1 Inclusion Criteria

Subjects who meet all the following inclusion criteria will be eligible to participate in the study:

1. Subject signs an IRB approved written informed consent and privacy language as per national regulations (e.g., Health Insurance Portability and Accountability Act authorization) before any study related procedures are performed.
2. Subject is a healthy man or woman, 18 to 55 years of age, inclusive, who has a body mass index of 18.5 to 29.9 kg/m², inclusive, at Screening.
3. Subject has normal medical history findings, clinical laboratory results, vital sign measurements, 12 lead electrocardiogram (ECG) results, and physical examination findings at Screening or, if abnormal, the abnormality is not considered clinically significant (as determined and documented by the investigator or designee).

4. Subject must have a negative test result for alcohol and drugs of abuse at screening and Check-in (Day -1).
5. Subject has a peripheral blood eosinophil count of ≥ 50 and ≤ 700 cells per microliter as measured by a standard hematology analyzer.
6. Female subjects must be of non-childbearing potential or, if they are of childbearing potential, they must: 1) have been strictly abstinent for 1 month before Check-in (Day -1) and agree to remain strictly abstinent for the duration of the study and for at least 1 month after the last application of study drug; OR 2) be practicing 2 highly effective methods of birth control (as determined by the investigator or designee; one of the methods must be a barrier technique) from at least 1 month before Check-in (Day -1) until at least 1 month after the end of the study.
7. Male subjects must agree to practice 1 highly effective method of birth control (as determined by the investigator or designee) from at least 1 month before Check-in (Day -1) until at least 1 month after the end of the study.
8. Subject is highly likely (as determined by the investigator) to comply with the protocol defined procedures and to complete the study.

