5.9.8.3 Vital Sign Measurements

Vital sign measurements and changes from baseline will be summarized using descriptive statistics (number of subjects, mean, SD, minimum, median, and maximum) by treatment and time point.

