5.9.8.4 Safety 12-lead Electrocardiograms

Safety 12-lead and telemetered ECG data and changes from baseline will be summarized using descriptive statistics (number of subjects, mean, SD, minimum, median, and maximum) by treatment and time point. The extent of change in each of the treatments will also be compared. The incidence of pathological ECG interpretive statements at Baseline and during treatment will be assessed among the treatments.

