7.7.2 Clinical Laboratory Tests

Clinical laboratory results (hematology, serum chemistry, and urinalysis) will be summarized using descriptive statistics (number of subjects, mean, SD, minimum, median, and maximum). Clinical laboratory results will be classified as normal or abnormal, according to the reference ranges of the individual parameter. No statistical testing will be performed on clinical laboratory data.

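### Laboratory safety summaries use neither the pre-dose value nor the direction of an abnormality, so the Protocol's abnormal count may include abnormalities present before dosing

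*Protocol*

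**What the plan says.** **Laboratory data, Protocol 5.9.8.2.** Three outputs are planned. The first is descriptive: "Clinical laboratory results (hematology, serum chemistry, and urinalysis) will be summarized using descriptive statistics (number of subjects, mean, SD, minimum, median, and maximum"). The second is the label: "Clinical laboratory results will be classified as normal or abnormal, according to the reference ranges of the individual parameter". The third is a count: the number and "percentage of subjects with abnormal laboratory results will be provided". The section does not say which time points enter the count or whether it is split by treatment.

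**Laboratory data, SAP 7.7.2.** The descriptive statistics and the two-class label are repeated, but the count is missing. The text passes straight from "reference ranges of the individual parameter. No statistical testing will be performed on clinical laboratory data".

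**Neighbouring safety data.** Protocol 5.9.8.3 says "Vital sign measurements and changes from baseline will be summarized using descriptive statistics", by treatment and time point, and SAP 7.7.3 does the same. Protocol 5.9.8.4 says "Safety 12-lead and telemetered ECG data and changes from baseline will be summarized using descriptive statistics", again by treatment and time point. SAP 7.7.4 keeps only the ECG interpretive statements, at baseline and during treatment.

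**Entry rules.** Inclusion criterion 3 (Protocol 5.2.1) admits laboratory findings that are out of range: "if abnormal, the abnormality is not considered clinically significant". Exclusion criterion 17 (Protocol 5.2.2) removes an out-of-range result only when the investigator also judges it clinically significant.

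**Pre-dose samples.** Hematology, chemistry and urinalysis are done at Screening (Protocol 5.6.2) and at Check-in on Day -1 (Protocol 5.6.3.1).

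**The concern.** A laboratory safety table should help the reader tell a change after dosing from a condition the volunteer brought into the study. As planned, the abnormal count has no such separation. A subject who was mildly out of range at Check-in and stays there can be counted exactly like one who moved out of range after dosing. The entry criteria make the first kind of subject foreseeable.

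The two-class label also drops direction. Hematology in Table 5-2 includes a white cell differential, and Protocol 2.1 describes a fall in circulating eosinophils as what these drugs do. A high count would mean something quite different, yet both directions fall in one class.

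With 8 subjects per arm, one such subject visibly moves the arm's percentage. A consistent shift that stays inside the reference range leaves no trace in the count and, without change from baseline, has to be found within between-subject spread. What is at stake is how readable the descriptive laboratory output is.

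**Working it through.** The plan states no figure on this point, so there is none to reproduce. The finding is textual, and the arithmetic below only shows its possible size.

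**1. Side-by-side reading**

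| Feature | Laboratory | Vital signs | ECG |
|---|---|---|---|
| Change from baseline | neither document | both documents | Protocol only |
| By treatment and time point | not stated | both documents | Protocol only |
| High/low split or shift table | neither document | not applicable | not applicable |
| Count of subjects abnormal | Protocol only | none | interpretive statements, at baseline and during treatment |

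**2. Chance that an arm already holds an out-of-range subject**

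Inputs: n = 8 per arm (Protocol Table 5-1). The pre-dose out-of-range proportion p for one analyte is not in the documents. I take 5% (a reference range covering 95% of healthy people) as the upper value, and 2.5% and 1% as lower values because screening removes clinically significant abnormalities.

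P(at least one of 8) = 1 − (1 − p)^8:

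- p = 1%: 1 − 0.99^8 = 7.7%; expected among 72 subjects, 72 × 0.01 = 0.7
- p = 2.5%: 1 − 0.975^8 = 18.3%; expected 1.8
- p = 5%: 1 − 0.95^8 = 33.7%; expected 3.6

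One subject is 1/8 = 12.5 percentage points of an arm.

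**3. Share of post-dose abnormalities that were there before dosing**

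Simulation, 400,000 subjects per setting. All inputs are assumptions: normally distributed values, limits at ±1.96 SD, no drug effect, within-subject correlation ρ of 0.5, 0.7 or 0.8, and k = 2, 4 or 8 post-dose tests. *Already abnormal* means out of range in the same direction before dosing. *New* means out of range after dosing in a direction in which the pre-dose value was not.

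| ρ | k | Any post-dose abnormality | Of these, already abnormal | New after dosing |
|---|---|---|---|---|
| 0.5 | 2 | 9.0% | 17% | 7.5% |
| 0.5 | 4 | 15.7% | 15% | 13.4% |
| 0.5 | 8 | 25.0% | 12% | 21.9% |
| 0.7 | 2 | 8.3% | 29% | 5.9% |
| 0.7 | 4 | 13.0% | 25% | 9.8% |
| 0.7 | 8 | 19.1% | 20% | 15.3% |
| 0.8 | 2 | 7.8% | 38% | 4.8% |
| 0.8 | 4 | 11.4% | 32% | 7.7% |
| 0.8 | 8 | 15.7% | 26% | 11.6% |

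So 12% to 38% of subjects abnormal after dosing were already abnormal in that direction. The other 62% to 88% were not: with no drug effect, the count of new abnormalities still flags 4.8% to 21.9% of subjects per analyte.

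**4. Gain from change from baseline**

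SD of change relative to SD of the raw value = √(2(1 − ρ)): 1.00 at ρ = 0.5, 0.77 at 0.7 and 0.63 at 0.8. There is no gain at 0.5, and a 23% to 37% smaller SD at 0.7 to 0.8.

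**The case against.** The strongest reply is that the plan has other ways to see laboratory problems.

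- The raw minimum and maximum keep some direction.
- Protocol 5.7.4.2 has every out-of-range value evaluated for clinical significance, with repeat tests where appropriate.
- An abnormal laboratory finding can be an adverse event, and a treatment-emergent event must begin after dosing (Protocol 5.7.4.1.1). The adverse event tables therefore separate before from after for findings recorded that way.
- All data are listed, so any flagged subject's pre-dose value can be looked up, and there is a concurrent placebo arm.
- Eosinophils have their own baseline-adjusted analysis as the primary PD biomarker, by flow cytometry. The documents give no eosinophil reference range, so it is not known whether a drug-lowered differential count would be labelled abnormal.
- Exclusion criterion 2 bars low hematocrit or hemoglobin outright, so 5% is too high for those analytes in that direction.

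All of this stands as mitigation. It rules out two stronger readings that a reader might infer. One is that laboratory safety is judged only against the reference range; the descriptive statistics, clinical review and adverse event route show otherwise. The other is that pre-existing abnormalities are counted as abnormal on drug. Protocol 5.9.8.2 names neither the time points nor a split by treatment, and the SAP does not carry the count at all, so the text supports only that they may be counted.

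The mitigation does not remove the gap. Adverse event onset does not reclassify the laboratory table, listings are not a planned summary, and a placebo arm of 8 leaves chance baseline differences in place.

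**Conclusion.** The point holds as a minor improvement to safety reporting. Neither document plans a baseline comparison or a directional split for laboratory data, although the pre-dose samples exist, the entry rules let non-significant abnormalities in, and the vital sign sections already use the better summary. The two documents also differ on whether abnormal results are counted.

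The size is modest and rests on assumed values of p, ρ and k. Per analyte, the chance that an arm holds at least one subject already out of range runs from 7.7% to 34%, and screening pushes it towards the lower end. The 12% to 38% already-abnormal share means that a count of new abnormalities removes a minority of the background, not most of it. No PD or PK endpoint, and no formal test, depends on this.

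**What to change.** In Protocol 5.9.8.2 and SAP 7.7.2:

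1. Summarise laboratory values and their changes from the last pre-dose value by treatment and time point, as for vital signs.
2. Give a low/normal/high shift table per analyte by treatment. Count abnormalities new after dosing, by direction and treatment, where new means out of range in a direction in which the pre-dose value was not. Read the hematology eosinophil count by direction, since a fall is the intended effect.
3. State in both documents whether the count of subjects with abnormal results is reported and, if it is, which time points enter it.

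The cost is revised wording and a few more descriptive safety tables. No extra samples, visits or subjects are needed.

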5.9.8.3 Vital Sign Measurements

Vital sign measurements and changes from baseline will be summarized using descriptive statistics (number of subjects, mean, SD, minimum, median, and maximum) by treatment and time point.

5.9.8.4 Safety 12-lead Electrocardiograms

Safety 12-lead and telemetered ECG data and changes from baseline will be summarized using descriptive statistics (number of subjects, mean, SD, minimum, median, and maximum) by treatment and time point. The extent of change in each of the treatments will also be compared. The incidence of pathological ECG interpretive statements at Baseline and during treatment will be assessed among the treatments.

5.9.8.5 Physical Examinations

Physical examination findings will be presented in a data listing, and abnormal physical examination findings will be recorded as AEs.

5.9.8.6 Other Safety Data

All concomitant medication usage and medications that changed in daily dose, frequency, or both since the subject provided informed consent will be summarized for each subject.

5.9.9 Interim Analyses

No interim analyses are planned.

5.9.10 Missing Data

Missing data will not be imputed. Data that are excluded from the descriptive or inferential analyses will be included in the subject data listings. This will include data from subjects not in the particular analysis population, measurements from unscheduled visits, or extra measurements that may arise from 2 or more analyses of the biofluid sample at the same time point.

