6.1. Handling of Missing and Incomplete Data

The following imputation of missing values will be done:

- Pharmacokinetic measurements below the quantification limits will be considered equal to zero for all analyses.
- Non-pharmacokinetic measurements (e.g., eosinophils) below the quantification limits will be considered equal to the lower limit of quantification for all analyses unless explicitly noted otherwise.
- Missing pharmacokinetic or pharmacodynamic data (e.g., skipped outpatient visit) will not be imputed.
- For baseline adjusted measures, samples from Day 1, time 0 will be used for calculating this derived metric. In cases where the Day 1, time 0 sample is missing or invalid, the sample collected at check-in (Day -1) will be used, followed by the screening sample. If none of these samples are available or valid, then no baseline value will be calculated for the subject.

7. General Statistical Considerations

All data will be presented in data listings. Data from subjects excluded from an analysis population will be presented in the data listings, but not included in the calculation of summary statistics. In addition, the reason for exclusion from an analysis population will be noted for individual subjects.

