7.7.4 Safety 12-lead Electrocardiograms

The incidence of pathological ECG interpretive statements at Baseline and during treatment will be assessed among the treatments.

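### Protocol 5.9.10 keeps unscheduled results out of the abnormal-laboratory count; separately, the SAP omits that count and the ECG change summaries

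*Protocol*

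**What the plan says.** **Unscheduled results.** Protocol 5.9.10 states: "Data that are excluded from the descriptive or inferential analyses will be included in the subject data listings". Its next sentence lists what this covers, including "measurements from unscheduled visits, or extra measurements that may arise from 2 or more analyses of the biofluid sample at the same time point". The section does not separate efficacy-type measurements from safety measurements, or means from counts. SAP 6.1 and SAP 7 neither repeat this rule nor withdraw it.

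**Laboratory output.** Protocol 5.9.8.2 ends its reporting plan with a count: the number and "percentage of subjects with abnormal laboratory results will be provided". SAP 7.7.2 keeps the descriptive statistics and the classification step ("Clinical laboratory results will be classified as normal or abnormal, according to the reference ranges of the individual parameter") but has no sentence reporting how many subjects fall in the abnormal class.

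**ECG output.** Protocol 5.9.8.4 promises three things:

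- "Safety 12-lead and telemetered ECG data and changes from baseline will be summarized using descriptive statistics", by treatment and time point;
- "The extent of change in each of the treatments will also be compared";
- the incidence of pathological readings.

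SAP 7.7.4 consists of the third item alone: "The incidence of pathological ECG interpretive statements at Baseline and during treatment will be assessed among the treatments".

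**The concern.** There are two separate points.

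First, leaving unscheduled values out of a by-visit mean is ordinary practice, because they belong to no nominal time point. A count of subjects with any abnormal result is different. It has no time-point structure to protect, and a valid post-dose value is informative whenever it was taken. A rule written without that distinction can classify a subject as not abnormal when an abnormal value is on file.

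Second, the SAP sets the tables that will be produced. If it classifies laboratory results but specifies no tally, and reduces ECG reporting to categorical readings, safety outputs promised in the Protocol may not appear in the report. A shift in ECG intervals that stays within normal limits would not show up in a count of pathological readings. It would show up in a change-from-baseline table.

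**Working it through.** No sample size, power or error rate is involved, so the check compares the texts.

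**Point 1: does 5.9.10 reach the abnormality count?**

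1. The count in Protocol 5.9.8.2 is a descriptive summary.
2. Protocol 5.9.10 names unscheduled-visit measurements among the data excluded from descriptive analyses and makes no safety exception.
3. Read literally, an abnormal value obtained only at an unscheduled visit therefore does not enter the 5.9.8.2 count.
4. The effect is limited to abnormalities first seen off schedule. A footnote to Protocol Table 9-1 says notable laboratory results are repeated, and 5.7.4.2 lets the investigator repeat tests. Leaving out such a repeat does not remove the scheduled value that prompted it, so that subject is still counted.
5. The same question arises for the incidence of pathological ECG readings, which is also a count and not a by-visit mean.

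**Point 2: which Protocol outputs does the SAP carry forward?**

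| Output | Protocol | SAP |
|---|---|---|
| Laboratory descriptive statistics | 5.9.8.2: yes | 7.7.2: yes |
| Normal/abnormal classification | 5.9.8.2: yes | 7.7.2: yes |
| Number and proportion of subjects abnormal | 5.9.8.2: yes | 7.7.2: absent |
| Vital signs and change from baseline | 5.9.8.3: yes | 7.7.3: yes |
| ECG/telemetry values and change from baseline | 5.9.8.4: yes | 7.7.4: absent |
| Comparison of extent of ECG change | 5.9.8.4: yes | 7.7.4: absent |
| Incidence of pathological ECG readings | 5.9.8.4: yes | 7.7.4: yes |

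The SAP therefore omits one laboratory output and two ECG outputs. It keeps the parallel vital-sign summary in full, so this is not a general trimming of safety reporting.

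**Other routes by which an abnormality would be seen.**

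- Listings: SAP section 7 says "All data will be presented in data listings". Listings show the value but give no incidence by treatment.
- Adverse events: the definition in Protocol 5.7.4.1.1 includes abnormal laboratory findings, 5.7.4.1.2 requires all adverse events to be recorded until discharge, and SAP 7.7.1 summarises their incidence with no restriction to scheduled visits.
- The adverse-event route is explicit only for physical examinations (Protocol 5.9.8.5, SAP 7.7.5). For laboratory and ECG abnormalities, Protocol 5.7.4.2 and 5.7.4.4 direct the subject to a personal physician and do not themselves call for an adverse-event entry.

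**Size.** The documents give neither the frequency of unscheduled tests nor any abnormality rate, so the under-count cannot be calculated.

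**The case against.** The case on the other side has real force. Protocol 5.9.10 governs measurements, not events, and a clinically relevant abnormality can reach the adverse-event tables whenever it was found. All data are listed. The only stated reason for extra laboratory tests is a notable result or the investigator's wish to repeat, and then the triggering value is already counted. SAP 7.7.2 still classifies each result, and its silence on the tally need not cancel the Protocol's promise. Heart rate is still summarised as a vital sign under SAP 7.7.3, so the ECG gap mainly concerns intervals and telemetry values. No study objective or endpoint is a safety one.

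Most of that stands and keeps the point small. It does not remove the point: the adverse-event tables do not replace a reference-range count, and a promise found only in the Protocol is easily missed when tables are programmed from the SAP.

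Four stronger readings are tempting but not supported:

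- A reader might infer that unscheduled results vanish from every summary and that safety abnormalities are therefore under-reported. The adverse-event tables contradict the first part, and the second is a possibility, not a demonstrated result.
- A reader might take one subject's weight in an arm, 1/8 = 12.5 percentage points, as the bias. It is only arithmetic on arm size and says nothing about how many subjects would be affected.
- A reader might treat the SAP change log's silence as evidence of an unrecorded removal. The log covers changes made in SAP version 2. It is not a list of differences from the Protocol, and the shorter text may already have stood in version 1.
- A reader might see the two points as compounding. Under the SAP as written no abnormality rate is specified, so the Protocol rule has none to lower. They would combine only if the count were restored and 5.9.10 left unchanged.

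**Conclusion.** Both points hold, separately, and both are minor.

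1. Taken literally, Protocol 5.9.10 keeps unscheduled-visit values out of the abnormal-laboratory count, so an abnormality first seen at such a visit would be listed, and might be an adverse event, but would not be counted. This rests on the literal reading of a section headed Missing Data; the authors may have meant only by-visit statistics, but the text does not say so. The size is unknown.
2. SAP 7.7.2 and 7.7.4 omit the abnormal-laboratory count and the ECG/telemetry descriptive and change summaries that the Protocol promises, and give no reason.

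The primary pharmacodynamic analysis is not affected by either point.

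**What to change.** - **Protocol 5.9.10** (or a clarifying sentence in SAP 6.1): limit the exclusion of unscheduled measurements to descriptive statistics by time point, so that abnormality counts use every valid post-dose value.
- **SAP 7.7.2:** restore the number and percentage of subjects with any post-dose abnormal laboratory result, by treatment, counting scheduled and unscheduled values. Protocol 5.9.8.2 states neither the time window nor the grouping, so the SAP should state both.
- **SAP 7.7.4:** restore descriptive statistics for ECG and telemetry values and their changes from baseline, by treatment and time point. Setting the treatments side by side also gives the comparison of change that the Protocol mentions.
- If the sponsor prefers not to produce any of these outputs, the SAP should record the departure from the Protocol and the reason.

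The cost is a few sentences and two or three standard safety tables from data the study already collects. No extra visits or samples are needed.
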